8.4. PHENOTYPING CONTRAINDICATIONS

Blood Draw / Venipuncture:

- Active infection over the site of blood draw
- Recent or recurrent history of fainting/vasovagal syncope with previous blood draws
- Lack of vascular access (inability to find venous access)

Stool collection:

None

Biomechanical Assessment:

- Inability to walk at least 50 feet unassisted
- Inability to stand for at least 10 minutes
- Participants with an allergy to adhesives will not have adhesive sensors placed on their body

Imaging:

- Certain implanted medical devices (e.g., implanted cardiac devices, cochlear implants, or intracranial aneurism clips)
- Ferrous metal (e.g., wire mesh, screws) in the body that will cause safety issues (titanium implants are acceptable)³⁸
- Waist circumference equal to or greater than the bore diameter of the study site scanner
- Pregnancy

QST:

- Peripheral neuropathy
- Participants with a history of Raynaud's Syndrome will not undergo cold-water immersion
- Participants with circulatory or sensory problem in the hands will not undergo cold-water immersion
- Participants with SBP ≥150 and/or DBP ≥100 will not undergo cold-water immersion

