Imaging: All participants will undergo Magnetic Resonance Imaging (MRI) of the spine. A subset of participants may undergo MRI of the brain and an additional spine MRI utilizing magnetic resonance spectroscopy. MRI is safe for most participants but is contraindicated for certain subsets of people, such as those with certain medical devices (e.g., implanted cardiac devices, cochlear implants, or intracranial aneurism clips) or with ferrous metal in their body (e.g., wire mesh, screws). MRI is not safe for pregnant women. While MRI is safe for most participants, the procedure may cause some participants to feel emotional discomfort, anxiety, and claustrophobia. The noise of MRI requires participants to wear ear protection and may cause peripheral muscle or nerve stimulation.

Quantitative Sensory Testing (QST): QST may cause minor but temporary physical discomfort. Specifically, the manual pressure algometer and pin prick stimulus are commonly used in QST studies and will not cause tissue injury at the maximum forces applied in this study. However, these instruments may cause minor physical discomfort in the areas of testing; this discomfort is expected to resolve within minutes of test completion. Conditioned Pain Modulation (CPM) assessments using cold stimuli are also uncomfortable but will be limited in intensity and duration to prevent tissue damage. The coldwater bath component of the QST assessment is contraindicated for certain participants with uncontrolled high blood pressure, heart conditions, and a history of Raynaud's Syndrome.

Genetic Analysis & Information: The risks related to genetic analyses can be to individuals or groups. These harms include stigmatization and impact insurability for life, disability, and long-term care insurance. If stored genetic information were re-connected to a participant's identity, personal information about the participant and the participant's health and risk of disease could become known to others. This could present unknown risks.

Risks Associated with Study Interventions and Run-in Activities

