Risk Assessment & Mitigation for Phenotypic Assessments

Participants will be screened for contraindications to any of the BEST phenotyping procedures prior to enrolling in the study. All phenotyping activities (e.g., quantitative sensory testing, biomechanical assessments, blood draws) will be performed by appropriately trained and, where applicable, licensed personnel). Participating sites will be staffed by researchers with expertise in the assessment and treatment of chronic low-back pain, and the DAC will be responsible for ensuring all staff are trained and certified as required by the protocol prior to study launch.

Questionnaires: To minimize patient burden associated with completing a large number of questionnaires, as much as is feasible without sacrificing the validity of the data, participants will be

allowed to complete most questionnaires online prior to a scheduled visit or phone call assessment. This will allow participants to complete the questionnaires at their home or location of choice and to break up completion of the questionnaires into multiple sessions at their discretion. Participants will be instructed that they can contact study staff if at any point they become distressed while completing a questionnaire due to a lack of clarity about one or more questions or general discomfort caused by responding. While the completion of questionnaires will be incentivized, all participants will be told that they have the option to terminate participation without penalty and/or will be assisted in arranging medical/psychiatric help, if necessary.

Blood Draw / Venipuncture: In order to minimize risk of infection, venipuncture will be performed by trained medical personnel using aseptic technique including handwashing before and after the procedure and the utilization of sterile kits and gloves. Alcohol will be swabbed over the region of venipuncture prior to the procedure and a sterile bandage will be applied following the procedure.

Stool collection: Instructions regarding the safe collection of stool will be provided with each stool collection kit.

Biomechanical Assessment: Biomechanical assessments will be supervised by trained staff. Participants will be instructed that they can contact study staff if at any point they become distressed while completing an assessment.

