Imaging: The primary established hazard associated with MR imaging is that the magnet exerts a strong force on metal objects. For this reason, metal objects are excluded from the vicinity of the magnet so that they will not become projectiles. In addition, each subject undergoes a standard screening procedure to determine whether they have any implanted materials that may pose a risk. If there is any doubt about the nature of any implanted material, the subject will not be scanned. Participants will be instructed to bring or wear clothing without metal fasteners and remove jewelry and any other metal objects from their body. Participants will wear foam earplugs or headphones to reduce the loud noises made by the scanner. Participants will be able to communicate with the examiner throughout the scan. If needed, the participant will be removed immediately from the scanner. MRI sessions will be conducted by trained personnel. Participants will be encouraged to contact the study team if they notice any unusual symptoms or untoward side effects. The investigators have extensive prior experience in the utilization of MRI for research. The MRI machine is operated within FDA guidelines so the potential for inducing peripheral nerve stimulation is low. Participants who report pregnancy will be excluded from MRI portion of the protocol.

Quantitative Sensory Testing (QST): Study personnel will be trained by the investigators to be sensitive to participant discomfort and concerns. Participants will be instructed that they can stop any QST procedure anytime that the pain or unpleasantness of the task becomes unbearable. All procedures have been thoroughly evaluated for reliability and safety, and are well tolerated by individuals with chronic pain, causing no more than temporary mild discomfort in the body regions that will be evaluated.

Genetic Analysis: Current federal law will help protect study participants from genetic discrimination in health insurance and employment.

Risk Assessment & Mitigation for Study Interventions

Participants will be screened for contraindications to any of the BEST study interventions prior to enrolling in the study. Participants who have a contraindication to a study intervention and who are

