8. STUDY POPULATION

8.1. STUDY INCLUSION CRITERIA

To be eligible, an individual must meet all of the following inclusion criteria:

- Ability to read and understand English
- Provision of signed and dated informed consent form(s)
- Willing and able to receive study-related messages and survey links via email
- Willing and able to receive study-related phone calls
- Age 18 years old or older
- Low-back pain for at least 3 months and occurring on at least half the days in the past 6 months
- Contraindicated to no more than one of the study interventions at the time of eligibility assessment(s)
- Eligible to receive at least three of the four study interventions and willing to receive any intervention for which they are eligible
- A PEG score 4 or higher prior to the Run-in period
- Willing and able to undergo required phenotyping as defined in Section 9
- Regular reliable access to an internet-enabled device such as a smart phone, tablet, or laptop computer
- Meet Run-in period engagement eligibility criteria:
 - Completion of two Run-in study information modules prior to period 1 randomization (Visit 0)
- Low-back pain more severe than pain in other parts of the body
- Available to complete the full study protocol (approximately 9 months)

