8.2. STUDY EXCLUSION CRITERIA

An individual who meets any of the following criteria will be excluded from participation in this study:

- Pregnant at the time of Visit 0 (Baseline)
- Affirmative participant response to any of the following conditions:
 - Progressive neurodegenerative disease
 - History of discitis osteomyelitis (spine infection) or spine tumor

- History of ankylosing spondylitis, rheumatoid arthritis, polymyalgia rheumatica, psoriatic arthritis, or lupus
- History of cauda equina syndrome or spinal radiculopathy with functional motor deficit (strength <4/5 on manual motor testing)
- Diagnosis of any vertebral fracture in the last 6 months
- Osteoporosis requiring pharmacologic treatment other than vitamin D, calcium supplements, or bisphosphonates.
- History of any bone-related cancer or cancer that metastasized to the bone
- Currently in treatment for any non-skin cancer or plan to start non-skin cancer treatment in the next 12 months
- History of any non-skin cancer treatment in the last 24 months
- Visual or hearing difficulties that would preclude participation
- Uncontrolled drug/alcohol addiction
- Individuals actively pursuing disability or workers compensation or involved in active personal injury-related litigation
- o Currently participating in another interventional pain study
- Any condition that, in the opinion of the investigator, would preclude the patient from being able to safely participate in in the trial

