8.3. STUDY INTERVENTION CONTRAINDICATIONS

ACT intervention contraindications

An individual who meets any of the following criteria will be excluded from being randomized to receive ACT during the study:

Currently receiving or intending to receive within the next few months any pain-specific
psychotherapy, e.g., Cognitive Behavioral Therapy, directed towards pain even if it is only a part
of the treatment, and delivered by a psychologist or social worker

Duloxetine intervention contraindications

An individual who meets any of the following criteria will be excluded from being randomized to receive duloxetine during the study:

- Pregnant: If the participant becomes pregnant during the study, duloxetine will be rapidly tapered.
- Currently taking any of the following:

Duloxetine

Lithium

Tramadol (Ultram, Ultracet)

St. John's Wort

Prochlorperazine (Compazine)

Thioridazine (a psychiatric medication)

Propafenone or Flecainide (for heart rhythm problems)

Ciprofloxacin (Cipro, an antibiotic)

Linezolid (Zyvox, an antibiotic)

Methylene Blue

Cimetidine (Tagamet, for heartburn)

Bupropion (Wellbutrin)

SNRIs:

Venlafaxine

Milnacipran

Duloxetine

Sibutramine

Atomoxetine

Desvenlafaxine

Levomilnacipran

SSRIs:

Sertraline

Paroxetine

fluoxetine

escitalopram

citalopram

fluvoxamine

Vortioxetine (Trintellix)

Any other contraindicated SNRIs, SSRIs, and antidepressants

Reporting a current or previous diagnosis of any of the following

Renal dysfunction

End-Stage Renal Failure

Hepatic dysfunction

- Previous allergic or other severe adverse reaction to duloxetine or, as determined by the site PI, a medicine with duloxetine cross-reactivity.
- History of bipolar disorder, manic episodes, or suicide attempts
- Currently breastfeeding

EBEM intervention contraindications

An individual who meets any of the following criteria will be excluded from being randomized to receive EBEM during the study:

- Currently receiving or intending to receive within the next few months any type of manual therapy or exercise treatment for low-back pain from a licensed provider
- Uncontrolled high blood pressure (≥150 systolic and/or ≥100 diastolic)
- Uncontrolled coronary artery disease
- Inability to walk at least 50 feet unassisted
- Contraindication for manual therapy
- Contraindication for participation in an exercise program

ESC intervention contraindications

An individual who becomes pregnant during the study will be counseled to stop NSAIDs.

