12.2. SAFETY ASSESSMENTS

Participants will be screened for contraindications to any of the BEST study interventions and phenotyping procedures prior to enrolling in the study. At the baseline visit, participant medical history will be obtained by the clinical coordinator and a physical assessment will be performed by a qualified medical professional. Basic safety assessments will be performed at 6 weeks (midpoint of intervention period one), 12 weeks (Visit 1), 18 weeks (midpoint of intervention period two), 24 weeks (Visit 2), and 36 weeks post-baseline (12 weeks after intervention period two) to assess participant tolerability to their current study intervention(s). Patients who are unable to tolerate their assigned study treatment will be educated on how to safely discontinue their current treatment plan but will otherwise remain in the study. Study staff will conduct an additional assessment of participants randomized to duloxetine via phone on day 7 (or next business day if falls on a weekend) of the intervention phase with participants newly randomized to duloxetine (i.e., day 7 of either the first or second intervention period).

Participants will be asked to report pregnancy status at multiple time points: prior to enrollment at Prescreening and Screening, and prior to randomization at the Baseline and 12-Week visits. Participants who report pregnancy prior to randomization to the first period intervention are excluded from the study. If the participant becomes pregnant during the study, duloxetine will be rapidly tapered. Participants who become pregnant during the study will not undergo study MRIs.

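### Protocol 5.2.1 treats some heart conditions as a contraindication to the cold-water bath, but the QST list in 8.4 has no cardiac rule

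*Protocol*

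**What the plan says.** Protocol 5.2.1, in its account of QST risks, says the cold-water bath is "contraindicated for certain participants with uncontrolled high blood pressure, heart conditions" and a history of Raynaud's. Protocol 5.2.3 then commits the sites to act on such contraindications: "Participants will be screened for contraindications to any of the BEST phenotyping procedures prior to enrolling in the study".

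The contraindications to each phenotyping procedure are listed in Protocol 8.4. Its QST list has four items. Peripheral neuropathy applies to QST as a whole. The other three apply to immersion only: a history of Raynaud's, circulatory or sensory problems in the hands, and blood pressure ("Participants with SBP ≥150 and/or DBP ≥100 will not undergo cold-water immersion").

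Protocol 9.6 describes the procedure. One hand is placed in circulating water at 10°C for 60 seconds as the conditioning stimulus for conditioned pain modulation (CPM). Section 9 schedules QST at three visits for those who take up the optional assessments.

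**The concern.** Of the three conditions the risk section names for the bath, the heart is the only one with no counterpart in the list that staff would screen from. A coordinator who applies 8.4 exactly as written has no prompt to withhold immersion from someone with a heart condition, even though 5.2.1 may regard that person as contraindicated.

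What is at stake is the safety of a small, unknown number of participants during one optional test. The estimation of the dynamic treatment regime does not depend on it.

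**Working it through.** No power or sample-size figure is involved, so the check is a comparison of texts followed by a test of whether the gap can be reached.

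**Step 1. The two sections side by side, for immersion.**

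| Condition | Named in 5.2.1 | Rule in 8.4 (QST) |
|---|---|---|
| High blood pressure | Yes | Yes, systolic ≥150 and/or diastolic ≥100 |
| Raynaud's | Yes | Yes |
| Heart conditions | Yes | None |
| Circulatory or sensory problems in the hands | No | Yes |

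Two of the three conditions named in 5.2.1 have a rule. Of the four QST items in 8.4, three are immersion-only and none is cardiac. The hand-circulation item does not reach coronary disease.

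**Step 2. How the protocol handles the same pairing elsewhere.** Protocol 5.2.1 uses nearly identical language for EBEM, pairing uncontrolled high blood pressure with heart conditions. There, 8.3 carries both halves into criteria: the same 150/100 cut-offs and "Uncontrolled coronary artery disease". For the bath, 8.4 carries over the cut-offs and has nothing for the heart. This points to an omission, although the documents do not say so.

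**Step 3. Can a participant reach the gap?** Take someone with uncontrolled coronary artery disease, blood pressure below 150/100, no implanted device and no other contraindication.

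- 8.3 bars this person from EBEM only.
- 8.1 tolerates one contraindicated intervention, so enrolment is possible.
- QST is open to those who opt into the additional phenotyping.
- No item in the 8.4 QST list applies.
- Neither 9.6, the QST paragraph of 5.2.3, nor the SAP adds a cardiac rule for immersion.

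The path is open unless someone exercises discretion.

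**Step 4. Exposure.** One immersion per visit × 3 visits = up to 3 immersions per affected participant, or 3 × 60 s = 180 s in total. The optional subset is about 200 in the Synopsis (4.1). Section 9 instead expects about one third of those enrolled, and 820 / 3 ≈ 273. Neither figure measures the number at risk, because no prevalence of heart conditions is given, so no study-wide total is offered.

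**The case against.** The strongest reply is that the protocol is not silent. Section 5.2.1 belongs to the same document, the screening commitment in 5.2.3 is not confined to 8.4, and the qualifier in 5.2.1 deliberately leaves room for clinical judgement. Several provisions support that judgement:

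- At baseline, "participant medical history will be obtained by the clinical coordinator and a physical assessment will be performed by a qualified medical professional". This gathers the information but attaches no immersion rule to it.
- 8.2 excludes for "Any condition that, in the opinion of the investigator, would preclude the patient from being able to safely participate", and 11.2 lets the study physician discontinue a participant whose interests are not served by continuing. Both work at the level of the whole trial. Neither tells staff to skip one test in someone otherwise fit to take part.
- Participants are told that "they can stop any QST procedure anytime that the pain or unpleasantness of the task becomes unbearable". That trigger is discomfort, not cardiac risk.
- Implanted cardiac devices are listed as an imaging contraindication in 8.4. Spine MRI is required of everyone, and Section 9 makes anyone contraindicated to a required assessment ineligible. A device that rules out MRI therefore keeps the person out of the trial altogether. This removes part of the cardiac population, but not coronary disease without a device.

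Two further points carry weight. The Manual of Procedures was not available and may hold a QST checklist with a cardiac item. No document establishes that uncontrolled coronary artery disease is the right threshold for a short hand immersion, which is why the clinical team must settle the wording. The exposure is also brief, and 9.6 allows for the hand coming out early.

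These points narrow the gap and limit its weight. None supplies the missing rule. The three immersion-only items already in 8.4 show that the authors did not rely on general discretion for this procedure.

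**Conclusion.** The inconsistency is real. The operative list omits a contraindication that the protocol's own risk section states, and following the list could lead to immersing someone whom the risk section treats as unsuitable. It should be corrected as a confined safety matter.

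Confidence is high on the textual mismatch. That staff would actually immerse such a person is a possibility and has not been shown; it assumes the Manual of Procedures adds no cardiac check and that no one invokes discretion. The SAP reports 805 participants already randomized, so the prospective benefit in this cohort may be limited. The correction still matters for any remaining visits and for any reuse of the procedure.

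**What to change.** Add one immersion-only line to the QST list in Protocol 8.4, for example:

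> Participants with uncontrolled coronary artery disease, or another heart condition for which the site investigator judges cold-water immersion unsafe, will not undergo cold-water immersion.

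The clinical team should confirm the wording. Leave the broader reference to heart conditions in 5.2.1 as it stands; narrowing it to coronary disease would remove protection. If the Manual of Procedures contains a QST checklist, bring it into line.

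Affected participants would still complete pressure pain sensitivity and temporal summation, as they would under the existing immersion-only rules. The cost is one line of text and up to three CPM values per affected participant, within the optional subset only.

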8.5. LIFESTYLE CONSIDERATIONS

Not applicable

8.6. SCREEN FAILURES

Screen failures are defined as participants who consent to participate in the clinical trial but are not subsequently randomly assigned to the study intervention or entered in the study. A minimal set of screen failure information is required to ensure transparent reporting of screen failure participants, to meet the Consolidated Standards of Reporting Trials (CONSORT) publishing requirements and to respond to queries from regulatory authorities. Minimal information includes demography, screen failure details, eligibility criteria, and any serious adverse event (SAE).

8.7. STRATEGIES FOR RECRUITMENT AND RETENTION

Study participants will be recruited from direct contact in clinical settings, screening via electronic health records (EHR) for chronic back pain, online surveys, and through community outreach. Sites may also choose to compensate current participants who refer others with cLBP that enroll and remain in the study. Site coordinators will generate a programmable phenotype based on the inclusion/exclusion criteria to generate a list of medical record numbers/unique patients to be screened. Site coordinators will use electronic health records (EHR) to search for ICD10 codes indicating the presence of chronic low back pain M54.40, M54.41, M54.42, M54.5, and M54.89 within the past 1 year in order to generate a list of medical record numbers/unique potential participants. Progress notes housed within the EHRs may also be searched by an algorithm for the presence of "low back pain," "back pain," or "lumbago" in order to generate a list of medical record numbers/unique potential participants. Site coordinators may use additional ICD10 codes and progress note keywords as they develop and identify effective search

parameters. The list of unique potential participants will be updated as frequently as daily such that new patients coming into the system with chronic low back pain or who develop chronic low back pain may be screened for eligibility. Patient's records will be further screened to determine if any exclusion criteria are met. Patients meeting the inclusion/exclusion criteria will be contacted via phone for the initial pre-screening call, sent a letter assessing interest in the study, or approached during a scheduled clinic visit as allowed by the site's regulatory guidelines.

Enrollment of a diverse sample will be monitored in real time to ensure overall enrollment approximates the US population experiencing low-back pain. The DAC will assess subgroup enrollment targets each month and instruct sites to adjust recruitment to correct under or overrepresentation of any particular subgroup.

Various approaches will be considered to enhance participant retention including scheduling flexibility, phone calls from the coordinators (or electronic messaging), updates on study progress (such as regular study newsletter targeted at the participants, celebrating milestones), and invitation to provide input into future studies.

Recruitment and retention throughout the study will be monitored by the DAC, which will oversee development of materials to facilitate recruitment and retention, monitor progress of both as the study progresses, and develop strategies for addressing recruitment and retention issues as they arise. The Data Safety and Monitoring Board (DSMB) will monitor accrual at each clinical center based on periodic summary reports provided by the DAC for their review (see Section 14.1.8) and make recommendations on proposals to address recruitment or retention challenges, such as adding clinical centers, if needed.

